15.2 Ascorbic Acid (Vitamin C, ASCOR®)

- 15.21 **Background:** Ascorbic acid (vitamin C), a water-soluble vitamin, is an essential coenzyme for collagen formation, tissue repair and synthesis of lipids and proteins. It acts both as a reducing agent and as an antioxidant and is necessary for many physiologic functions such as metabolism of iron and folic acid, resistance to infection, and preservation of blood vessel integrity.
- 15.22 **Formulation:** ASCOR® (ascorbic acid injection) 25,000 mg/50 mL (500 mg/mL) for intravenous use is a colorless to pale yellow, preservative-free, hypertonic, sterile, non-pyrogenic solution of ascorbic acid. [49] ASCOR must be diluted with an appropriate infusion solution (e.g. 5% Dextrose Injection, USP, Sterile Water for Injection, USP). Each ASCOR, 50 mL, Pharmacy Bulk Package vial contains 25,000 mg ascorbic acid, equivalent to 28,125 mg sodium ascorbate. Each mL of ASCOR contains 500 mg of ascorbic acid (equivalent to 562.5 mg of sodium ascorbate which amounts to 65 mg sodium/mL of ASCOR), 0.25 mg of edetate disodium, and water for injection. Sodium hydroxide and sodium bicarbonate are added for pH adjustment (pH range 5.6 to 6.6). It contains no bacteriostatic or antimicrobial agent.

15.23 Preparation and storage:

Penetrate each PBP vial closure **only one time** with a suitable sterile transfer device or dispensing set that allows measured dispensing of the contents. Given that pressure may develop within the vial during storage, exercise caution when withdrawing contents from the vial. Once the closure system has been penetrated, **complete all dispensing from the PBP vial within 4 hours**. Each dose **must be used immediately**. Discard unused portion.

Store vials in a refrigerator at 2°C to 8°C (36°F to 46°F). Protect vials from light and product has an expiration of 24 hours at room temperature. This product contains no preservative.

- 15.24 Administration:** Do not administer ASCOR as an undiluted intravenous injection. Administer 750mg – 1000 mg/minute as outlined in Section 7.1. Start infusion rate at 0.75g/minute. If no dizziness after 15 minutes the rate can be increased to 1 g/min. Infusion times are approx. (± 15 minutes) and may need to be adjusted based on patient tolerability. The maximum allowed dose is 100 g per infusion.

15.25 Pharmacokinetic information:

Distribution: Ascorbic acid is distributed widely in the body, with large concentrations found in the liver, leukocytes, platelets, glandular tissues, and lens of the eye. Based on data from oral exposure, ascorbic acid is known to be distributed into breast milk and crosses the placental barrier.

Metabolism: A major route of metabolism of ascorbic acid involves its conversion to urinary oxalate, presumably through intermediate formation of its oxidized product, dehydroascorbic acid.

Elimination: When the body is saturated with ascorbic acid, the plasma concentration will be about the same as that of the renal threshold; if further amounts are then administered, most of it is excreted in the urine. When body tissues are not saturated and plasma concentration is low, administration of ascorbic acid results in little or no renal excretion. The mean \pm SD (N=3) half-life observed in the single dose PK study as described above, was 7.4 \pm 1.4 h.

Excretion:

There is a renal threshold for ascorbic acid (Vitamin C); the vitamin is excreted by the kidney in large amounts only when the plasma concentration exceeds this threshold, which is approximately 1.4 mg/100 mL.

15.26 Potential Drug Interactions:

Antibiotics: Ascorbic acid may decrease activities of erythromycin, kanamycin, streptomycin, doxycycline, and lincomycin. Bleomycin is inactivated in vitro by ascorbic acid. If the antibiotic efficacy is suspected to be decreased by concomitant administration of ASCOR, discontinue ASCOR administration.

Amphetamine & Other Drugs Affected by Urine Acidification: Ascorbic acid may acidify the urine and lower serum concentrations of amphetamine by increasing renal excretion (as reflected by changes in amphetamine urine recovery rates). In case of decreased amphetamine efficacy discontinue ASCOR administration. Standard monitoring of therapy is warranted.

In addition, acidification of urine by ascorbic acid will alter the excretion of certain drugs affected by the pH of the urine (e.g. fluphenazine) when administered concurrently. It has been reported that concurrent administration of ascorbic acid and fluphenazine has resulted in decreased fluphenazine plasma concentrations. Standard monitoring of therapy is warranted.

Warfarin: Limited case reports have suggested interference of ascorbic acid with the anticoagulation effects of warfarin, however, patients on warfarin therapy treated with ascorbic acid doses up to 1000 mg/day (5 times the largest recommended single dose) for 2 weeks (twice the maximum recommended duration), no effect was observed. Standard monitoring for anti-coagulation therapy should continue during ascorbic acid treatment, as per standard of care.

Laboratory Test Interference: Because ascorbic acid is a strong reducing agent, it can interfere with numerous laboratory tests based on oxidation-reduction reactions (e.g. glucose, nitrite and bilirubin levels, leukocyte count, etc.). Chemical detecting methods based on colorimetric reactions are generally those tests affected. Ascorbic acid may lead to inaccurate results (false negatives) obtained for checking blood or urinary glucose levels, nitrite, bilirubin, and leukocytes if tested during or within 24 hours after infusion.

15.27 Known potential toxicities:

Most common adverse reactions are pain and swelling at the site of infusion.

Patients with glucose-6-phosphate dehydrogenase deficiency are at risk of severe hemolysis; a reduced dose is recommended.

Hot flashes, headache, fatigue, insomnia, stomach cramp, nausea and vomiting.

Allergy to ascorbic acid is extremely rare. Four cases of respiratory and cutaneous allergies to ascorbic acid have been documented.

Too rapid intravenous injection can cause temporary dizziness or faintness.

Acidification of urine by large doses of ascorbic acid might cause precipitation of urate, oxalate or cystine stones or drugs in the urinary tract, especially since some ascorbate is metabolized to oxalate. Some patients with pre-existing renal disease have been reported to develop renal failure following treatment with high doses of ascorbic acid.

High dosage of ascorbic acid may cause diarrhea.

Deep-vein thrombosis has been reported after large doses of ascorbic acid.

Rarely, decreased blood pH leading to sickle-cell crisis has been reported in patients with sickle cell disease.

At doses of greater than 600 mg, ascorbic acid has been reported to have a diuretic action. High doses can increase serum cholesterol in atherosclerotic patients.

15.28 Drug procurement:

The ascorbic acid will be purchased from McGuff Pharmaceuticals and supplied to Clinic Research Services, a division of Rx Crossroads by McKesson. Each participating ACCRU treating location will order the drug from Clinic Research Services, a division of Rx Crossroads by McKesson.

Fax the Drug Order Request Form (found on the ACCRU web site) to:

Each participating ACCRU treating location will be responsible for monitoring the supply of ascorbic acid and will use the appropriate Drug Order Request Form to order additional supplies as needed.

Outdated or remaining drug is to be destroyed on-site as per procedures in place at each institution.

15.29 Nursing Guidelines:

- 15.291 There are several possible drug- to drug interactions. Assess patient's concomitant medications including OTC and herbal products and cross-reference with section 15.16 in the protocol to assess for interactions.
- 15.292 Patients may experience hot flushes.
- 15.293 Headache is a possibility. Treat symptomatically and monitor for effectiveness.
- 15.294 If given IV, give over at least 15 minutes. Too rapid of infusion can cause dizziness and feeling faint. Some patients may need to have infusion slowed based on tolerability.
- 15.295 Rarely in patients who have a history of sickle-cell disease, patients could experience sickle cell crisis.
- 15.296 Patients who have renal impairment may be at higher risk of renal failure with higher doses. Monitor renal function closely and inform study team of any increases in creatinine. Additionally patients may be at higher risk of stones. Patients with a history of renal stones/calculi should be monitored closely.
- 15.297 Higher doses have been associated increases in serum cholesterol. Patients who have a history of hyperlipidemia may require additional monitoring as needed.

16.0 Statistical Considerations and Methodology**16.1 Overview:**

This is a randomized Phase II study which assess the efficacy of IV ascorbic acid in combination with Pazopanib (Arm A) when compared to Pazopanib alone (Arm B) in patients with metastatic/unresectable clear cell Renal Cell Carcinoma (ccRCC). Patients will be randomized at the time of registration at 1:1 ratio to either arm using a dynamic allocation procedure which balances the marginal distributions of the stratification factors (see Section 5) between the treatment regimens.

16.11 Primary Endpoint:

The primary endpoint of this trial is the Treatment Failure-Free rate at 40 week (TFF40). Treatment failure is defined as any of the following: radiographic disease progression, off-protocol treatment due to adverse event, initiation of alternative therapy (except metastatectomy post clinical benefit (CR, PR, or SD per RECIST 1.1) to treatment), and death due to any cause. Treatment failure-free rate at 40 weeks is defined as the proportion of evaluable patients who are not treatment failure at 40 weeks post randomization. All patients meeting the eligibility criteria who have signed a consent form and have received any protocol treatment will be considered evaluable. All eligible patients will be followed for disease evaluation until PD or a maximum of 2 years post-randomization then go to event monitoring for a maximum of 3 years post-randomization.

16.2 Statistical Design

16.21 Sample Size and Power:

Based on a study conducted by Motzer et. al, the median duration of pazopanib treatment was 8 month which is approximately equal to a TFF40 rate of 45%. A total of 82 eligible patients (41 in the IV ascorbic acid plus Pazopanib arm and 41 in the Pazopanib only arm) will provide 81% power to detect a 19% increase of TFF40 from 45% (in Pazopanib only arm) to 64% (in the IV ascorbic acid plus Pazopanib arm) assuming a one-sided type I error rate of 0.19 (EAST 6.4). We anticipate accruing an additional 9 patients to account for ineligibility, cancellations, and major violation for a maximum sample size of 91 patients.

16.22 Accrual Time and Study Duration:

The anticipated accrual rate is approximately 5 patients per month. Therefore, the accrual period for this randomized phase II study is expected to be 18.2. The final analysis can begin approximately 27.7 months after the trial is activated, i.e. as soon as the last patient has been observed for 40 weeks.

16.23 Operating Characteristics:

This randomized phase II design has a significance level of 0.19 when the true success proportion is 45%, and a power of 81% for detecting a true success proportion of 64%, assuming that the number of successes is binomially distributed. The probability of declaring that this regimen warrants further study (i.e. statistical power) under various success proportions can be tabulated as a function of the true success proportion as follows:

True TFF40 rate †		%‡ of times that Pazopanib+IV ascorbic acid is superior at the final analysis
Pazopanib only	Pazopanib+IV ascorbic acid	
45%	45%	18.34
45%	55%	47.93
45%	64%	79.45

‡ Proportions are based on 10,000 replicates in the simulation study

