13.6 A patient is deemed a *major violation*, if protocol requirements regarding treatment in cycle 1 of the initial therapy are severely violated that evaluability for primary end point is questionable. All data up until the point of confirmation of a major violation must be submitted. The patient will go directly to the event-monitoring phase of the study. The patient may continue treatment off-protocol at the discretion of the physician as long as there are no safety concerns, and the patient was properly registered. Event monitoring will be required per Section 18.0 of the protocol.

13.7 A patient is deemed a *cancel* if he/she is removed from the study for any reason before any study treatment is given. On-study material and the Off Treatment Form must be submitted. No further data submission is necessary.

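### Treated major violators count in the TFF40 denominator, but the sample size budgets them as losses and 13.6 takes them off the 8-weekly disease assessment that 16.11 promises

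*Combined protocol and SAP*

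**What the plan says.** Section 16.21 sets the target at 82 eligible patients, 41 per arm, and adds an "additional 9 patients to account for ineligibility, cancellations, and major violation", "for a maximum sample size of 91 patients". The allowance is one total for the three reasons, with no split.

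Section 16.11 says that eligible, consented patients who "have received any protocol treatment will be considered evaluable". Section 16.3 repeats this definition for the efficacy analysis. Neither section excludes major violators.

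Section 13.6 defines a major violation as one in which cycle 1 treatment requirements are so "severely violated that evaluability for primary end point is questionable". It requires data up to confirmation of the violation and continues: "The patient will go directly to the event-monitoring phase of the study". The patient may continue treatment off protocol. Section 13.3 sets event monitoring at every 6 months, plus or minus 30 days.

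Section 16.11 also says that all eligible patients have disease evaluation until progression or 2 years after randomization. The schema has CT every 8 weeks over the same span.

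TFF40 is the proportion of evaluable patients who are not treatment failures at 40 weeks. The failure components are radiographic progression, leaving protocol treatment because of an adverse event, starting alternative therapy (with an exception for metastasectomy after clinical benefit), and death. Major violation is not a component, and no rule covers a patient whose 40-week status is unknown.

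**The concern.** The plan gives three answers about the same patients. The sample size treats them as lost, the analysis set counts them, and the follow-up rules both withdraw and promise the assessments on which the primary endpoint depends.

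A site that follows 13.6 stops protocol scans for a patient who still counts in the primary analysis. Because TFF40 is defined by the absence of a failure, a violator with nothing on record can be read as failure-free. If such patients are unevenly split between arms, the comparison shifts for reasons unrelated to treatment, in a trial where a handful of patients can change the decision.

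**Working it through.** **1. Who is lost under each rule.** An ineligible patient fails the eligibility condition in 16.11. A cancelled patient (13.7) leaves before any treatment and so fails the treatment condition. An eligible patient who started cycle 1 and then became a major violator meets every condition. Two of the three reasons for the allowance therefore match the analysis set, and the third does not.

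**2. When a violator would be seen.** Event monitoring falls at about weeks 26 and 52. The window of 30 days is 30/7 = 4.3 weeks, so contacts fall in about weeks 22 to 30 and 48 to 56. Week 40 lies in neither.

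**3. The plan's own figures.** Inputs from 16.21 are 41 per arm, 45% against 64%, "assuming a one-sided type I error rate of 0.19", and 81% power. Section 16.3 specifies the normal approximation with un-pooled variance.

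- Standard error = √(0.45×0.55/41 + 0.64×0.36/41) = 0.1080.
- Power = Φ(0.19/0.1080 − 0.878) = Φ(0.882) = 81.1%, which reproduces the stated 81%.
- 82 + 9 = 91, as stated.

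**4. Does keeping violators leave the trial short?** No. If all 9 were violators who are kept and assessed (an upper bound), there would be 91/2 = 45.5 per arm. The standard error is then 0.1025, and power = Φ(0.19/0.1025 − 0.878) = Φ(0.976) = 83.5%.

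**5. Effect if violators are scored failure-free.** Let *a* of the 41 in Arm A and *b* of the 41 in Arm B be fixed as successes, with the rest binomial. The probability of z ≥ 0.878 is summed over all outcomes, where z is the difference in proportions divided by its un-pooled standard error. The values of *a* and *b* are assumptions.

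| Violators, A / B | Chance of promising, 45% in both arms | Power, 64% v 45% |
|---|---|---|
| 0 / 0 | 0.219 | 0.834 |
| 3 / 0 | 0.338 | 0.891 |
| 0 / 3 | 0.122 | 0.730 |
| 2 / 2 | 0.213 | 0.818 |
| 3 / 3 | 0.210 | 0.809 |

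In the 3 / 0 case, Arm A's expected rate under no effect is (0.45×38 + 3)/41 = 49.0% instead of 45%. The baseline of 0.219 is what exact enumeration gives for this test with no violators, so the other rows should be compared with it and not with the nominal 0.19.

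**6. Effect if they are scored as failures instead.** With three unassessed violators in Arm A and none in Arm B, Arm A's expected rate under the alternative is 0.64×38/41 = 59.3%, and power falls from 0.834 to 0.709.

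**The case against.** The strongest reply is that 16.11 already promises disease evaluation to all eligible patients until progression or 2 years, and the schema agrees. Event monitoring is also not blind to failure. The forms in 18.1 collect disease status every 6 months and at progression, documentation of progression, non-protocol treatment, and death. A progression dated before week 40 but reported later would still count. Both points stand. They show that the documents contradict each other on follow-up, not that these patients' outcomes go unrecorded.

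A reader might infer that violators will be counted as successes. The documents do not say so. They give no rule for unknown status, 13.6 itself doubts these patients' evaluability, and the allowance suggests that they were meant to be excluded. Counting them as failure-free is only the literal reading when no event is recorded.

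A reader might also infer a bias towards Arm A, because infusions three times a week offer more ways to breach cycle 1. The documents give no violation rates by arm. Section 7.1 tolerates missed and adjusted infusions, and more than 4 missed doses in a cycle leads to consultation, not automatic removal. Arm A patients who come off protocol treatment because of an adverse event are already failures. The direction is not established, and with equal numbers in each arm false-promising results do not increase.

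Finally, major violators are not the only such group. Under 13.3, patients who refuse treatment also go to event monitoring, and refusal is not a failure component. This supports a general rule for unknown status and does not remove the conflict over violators.

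**Conclusion.** The inconsistency is real and should be corrected. The allowance in 16.21 does not match the analysis set in 16.11 and 16.3, and 13.6 with 13.3 contradicts 16.11 and the schema on follow-up. A site that follows 13.6 leaves the primary endpoint poorly measured for patients who count in it.

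The size is conditional. Three violators scored failure-free in one arm only would move the chance of a false promising result from 0.219 to 0.338 or to 0.122, depending on the arm. Three in each arm leave it at 0.210 and lower power from 0.834 to 0.809. These figures assume that every violator is scored a success, so they are limits for the counts shown. Any failure captured in event monitoring reduces the effect. The number of violators and their split are not in the documents. Sample size is adequate whether violators are excluded or kept and assessed.

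**What to change.** 1. Reconcile 13.6 with 16.11 so that major violators who remain evaluable stay on the already planned 8-weekly disease assessment until progression or at least week 40.
2. State in 16.11 and 16.3 that treated, eligible major violators are in the primary analysis set.
3. Remove major violation from the reasons for the 9-patient allowance in 16.21. This does not reduce power.
4. For any evaluable patient whose 40-week status is still unknown, prespecify the handling in the primary analysis. Report two sensitivity analyses: counted as failure, and excluded as missing.

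The cost is protocol and SAP wording, plus a few more scans on the existing schedule. Scoring unknown status as failure is a trade-off: it lowers TFF40 in whichever arm has more unassessed patients, with the loss of power shown in step 6 of the working if they are all in Arm A. It should therefore be one of the reported extremes and not a substitute for obtaining the assessment.

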16.32 Definitions and Analyses of Secondary Endpoints

16.321 Overall Survival

Survival time is defined as the time from randomization to death due to any cause. Patients who are alive will be censored for death at the time of last known alive. All patients meeting the eligibility criteria that have signed a consent form and begun treatment will be considered evaluable for estimation of the survival distribution. The distribution of survival time will be estimated using the method of Kaplan-Meier and be compared using log rank tests.

16.322 Progression Free Survival

Progression Free Survival is defined as the time from start of study therapy to documentation of disease progression or death, whichever comes first. Patients who are still alive and have not progressed will be censored for progression at the time of the last tumor assessment. All patients meeting the eligibility criteria that have signed a consent form and begun treatment will be considered evaluable for estimation of the survival distribution. The progression free survival distribution will be estimated using the Kaplan-Meier method.

16.323 Overall Response Rate

A tumor response is defined to be a CR or PR noted as the objective response (according to RECIST v. 1.1) All patients meeting the eligibility criteria who have signed a consent form and have begun treatment will be evaluable for response. The best objective response rates between the two arms will be compared using a Chi-Square test.

16.324 Duration of time on pazopanib

Duration of time on pazopanib is defined as the time from initial dose of

pazopanib until the date the patient is considered off-treatment for pazopanib or death, whichever comes first. Only patients received at least 1 dose of pazopanib will be considered evaluable for this analysis. The time on pazopanib will be described using descriptive statistics.

16.325 Adverse events:

As per NCI CTCAE version 4.0, the term toxicity is defined as adverse events that are classified as either “possibly,” “probably,” or “definitely related” to study treatment. The maximum grade for each type of toxicity will be recorded for each patient, and frequency tables will be reviewed to determine toxicity patterns within patient groups. In addition, we will review all adverse event data that is graded as 3, 4, or 5 and classified as either “unrelated” or “unlikely to be related” to study treatment in the event of an actual relationship developing.

Adverse events and toxicities will be evaluated using all patients who have received any study treatment as well as summarizing those who have been included in the efficacy analyses. The overall adverse event rates for grade 3 or higher adverse events will be compared using Chi-Square tests between the 2 treatment arms.

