High dose vitamin C is known to be well tolerated and to have negligible side effects in patients with preserved renal function [33, 34] and has been shown in many studies to improve the quality of life in advanced cancers.[35-37] Multiple phase I clinical trials of intravenous ascorbate in patients with advanced cancer measured plasma concentrations of ascorbate and evaluated clinical consequences. [33, 38, 39] In the study by Riordan and colleagues, patients were given continuous infusion of 0.15 to 0.7 g kg⁻¹ day⁻¹ for up to eight weeks; in the Hoffer study, ascorbate was administered three times per week at fixed doses of 0.4, 0.6, 0.9 and 1.5 g kg⁻¹; and in the most recent study by Monti et al., patients received 50, 75 and 100 g per infusion (three infusions per week) for 8 weeks with concomitant IV gemcitabine and oral erlotinib. In the Riordan study, ascorbate concentrations in serum during therapy ranged from 0.28 to 3.8 mM. In the Hoffer study, peak plasma ascorbate concentrations ranged from 2.4 to 26 mM. When 1.5 g kg⁻¹ was administered, plasma ascorbate concentrations exceeded 10 mM for \approx 4.5 h, levels that have been shown to induce cell killing in a variety of cancer cells [40, 41]. Finally in the Monti study, patients that received 100 g of ascorbate achieved peak plasma concentrations between 25 and 32 mM. All three trials demonstrated that high-dose intravenous ascorbate was well tolerated in cancer patients with normal renal function; the combination of ascorbate infusion with standard of care chemotherapies did not increase toxicity.

Since high dose intravenous vitamin C has been studied in combination with TKI sorafenib in hepatocellular carcinoma [42] and shown to be safe, we think it would be reasonable to conduct a phase 2 study with the therapeutic dose established in the phase 1 studies.

1.4 Proposal Hypotheses:

1. Combining high dose IV ascorbic acid with pazopanib for the first line treatment of clear cell metastatic ccRCC will result in improved treatment failure-free rate at 9 months, median progression-free survival, objective response rate, tolerance and duration on therapy compared to pazopanib alone.

Exploratory Hypotheses:

2. Patients with ccRCC having higher iron content in the tumor micro-environment, as determined by iron staining using Prussian blue reaction, will have a better response to the combination of IV ascorbic acid and pazopanib than those with lower iron content.

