2.0 Goals

2.1 Primary Objective:

To estimate and compare treatment failure-free rate at 40 weeks from randomization of patients with unresectable/metastatic clear cell Renal Cell Carcinoma (ccRCC) receiving one of the following regimens:

- Arm A: Pazopanib 800mg daily plus intravenous (IV) ascorbic acid 1g/kg 3 times/week.
- Arm B: Pazopanib 800mg daily

2.2 Secondary Objective:

- 2.21 To estimate and compare the overall survival (OS) in patients receiving pazopanib with or without IV ascorbic acid
- 2.22 To estimate and compare the progression-free survival (PFS) in patients receiving pazopanib with or without IV ascorbic acid
- 2.23 To estimate and compare the overall response rate (ORR) in patients receiving pazopanib with or without IV ascorbic acid
- 2.24 To estimate and compare the duration on pazopanib treatment in patients receiving pazopanib with or without IV ascorbic acid
- 2.25 To assess the adverse events (AE) profile and safety of each treatment arm using the CTCAE

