6.12 Correlative Research

A mandatory correlative research component is part of this study, the patient will be automatically registered onto this component (see Sections 3.19 and 17.2).

- 6.13 Documentation of IRB approval must be on file in the Registration Office before an investigator may register any patients. Approvals should be uploaded using the online ACCRU Regulatory Management System (ARMS).

In addition to submitting initial IRB approval documents, ongoing IRB approval documentation must be on file (no less than annually) with ACCRU. Approvals should be uploaded using online ACCRU Regulatory Management Systems (ARMS) If the necessary documentation is not submitted in advance of attempting patient registration, the registration will not be accepted and the patient may not be enrolled in the protocol until the situation is resolved.

Submission of annual IRB approvals is required until the study has been closed through your IRB.

- 6.14 Prior to accepting the registration/randomization, the registration/randomization application will verify the following:
- IRB approval at the registering institution
 - Patient eligibility
 - Existence of a signed consent form
 - Existence of a signed authorization for use and disclosure of protected health information
- 6.15 At the time of registration, the following will be recorded:
- Patient has/has not given permission to store and use his/her tissue sample(s) for future research to learn about, prevent, or treat cancer.
 - Patient has/has not given permission to store and use his/her tissue sample(s) for future research to learn, prevent, or treat other health problems (for example: diabetes, Alzheimer's disease, or heart disease).
 - Patient has/has not given permission for ACCRU to give his/her tissue sample(s) to outside researchers.
- 6.16 Treatment cannot begin prior to randomization and must begin ≤ 14 days after randomization.
- 6.17 Pretreatment tests/procedures (see Section 4.0) must be completed within the guidelines specified on the test schedule.
- 6.18 All required baseline symptoms (see Section 10.52) must be documented and graded.
- 6.19a Treatment on this protocol must commence at an ACCRU institution under the supervision of a medical oncologist.
- 6.19b Study drug is available on site.
- 6.2 Randomization Procedures
- 6.21 The factors defined in Section 5.0, together with the registering membership, will be used as stratification factors.

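### Objective 2.22 calls for a between-arm comparison of PFS, but Section 16.322 plans only Kaplan-Meier estimation (2.24 has the same gap); the PFS clock also differs from that of OS and TFF40

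*Combined protocol and SAP*

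**What the plan says.** **Objective and hypothesis.** Objective 2.22 reads "To estimate and compare the progression-free survival (PFS) in patients receiving pazopanib with or without IV ascorbic acid". Hypothesis 1 in Section 1.4 expects the combination to improve, among other outcomes, "median progression-free survival, objective response rate, tolerance and duration on therapy compared to pazopanib alone".

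**PFS analysis.** Section 16.322 sets the time origin: "Progression Free Survival is defined as the time from start of study therapy to documentation of disease progression or death, whichever comes first". The planned analysis is one sentence: "The progression free survival distribution will be estimated using the Kaplan-Meier method".

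**Neighbouring endpoints.** For OS, Section 16.321 states that "Survival time is defined as the time from randomization to death due to any cause" and that "The distribution of survival time will be estimated using the method of Kaplan-Meier and be compared using log rank tests". Section 16.323 compares response between arms with a chi-square test. The primary endpoint in Section 16.11 is the "proportion of evaluable patients who are not treatment failure at 40 weeks post randomization". Section 16.324 describes time on pazopanib with descriptive statistics, although objective 2.24 is also worded as a comparison.

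**Gap between the two clocks.** Section 6.16: "Treatment cannot begin prior to randomization and must begin ≤ 14 days after randomization".

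**Analysis population.** Section 16.3 limits all efficacy analysis to patients who are eligible, consented and have received some protocol treatment.

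**The concern.** A reader who follows Section 16.322 to the letter produces a Kaplan-Meier analysis of PFS and stops. Objective 2.22 then has no pre-specified answer. If a comparison is added later, the test, effect measure, sidedness, alpha and any stratification would be chosen after the data are in hand.

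PFS has a particular use in this trial. TFF40 counts stopping treatment for an adverse event and starting alternative therapy as failures, and the trial is open-label (Section 1.5). PFS counts only progression and death, so it helps show whether a TFF40 difference reflects tumor control or treatment decisions. That needs a between-arm effect estimate fixed in advance.

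The time origin matters less. Measuring PFS from a post-randomization date gives the same patient a different clock for PFS than for OS and TFF40, and lets any start delay that differs by arm enter the comparison.

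**Working it through.** **1. Objectives against planned methods**

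| Objective | Wording | Time origin | Between-arm method |
|---|---|---|---|
| 2.21 OS | estimate and compare | randomization | log-rank (16.321) |
| 2.22 PFS | estimate and compare | start of therapy | none (16.322) |
| 2.23 ORR | estimate and compare | not applicable | chi-square (16.323) |
| 2.24 duration on pazopanib | estimate and compare | first dose | none (16.324) |

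Two of four have no comparative method. No general sentence fills the gap. The one sentence in Section 16.3 that compares secondary endpoints contrasts patients with prior immunotherapy against those with no prior systemic therapy, not Arm A against Arm B.

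**2. The plan's own figure.** The plan gives no power, event count or alpha for PFS. Its only power figure is 81% for TFF40 (Section 16.21: 41 per arm, 45% against 64%, one-sided 0.19). With the unpooled variance of Section 16.3:

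- SE = √(0.45×0.55/41 + 0.64×0.36/41) = 0.108
- Power = Φ(0.19/0.108 − 0.878) = Φ(1.760 − 0.878) = 0.811

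This reproduces. It concerns the primary endpoint and does not bear on the PFS gap.

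**3. Would there be enough events for a comparison?** This is an illustration, because the documents give no PFS design.

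- From the documents: 41 per arm (16.21); 18.2 months' accrual and analysis at 27.7 months (16.22); progression follow-up to 24 months (16.11); a 9-month median time to progression on pazopanib (1.5).
- Assumed: exponential PFS with that median as the control value, uniform accrual, no dropout.
- HR implied by the TFF40 target under proportional hazards: ln 0.64 / ln 0.45 = 0.56.
- Event probability in an arm: the average over accrual time u of 1 − exp(−λ·min(27.7 − u, 24)), with control λ = ln 2/9 = 0.0770 per month. The control arm gives 0.737. Arm A at HR 0.56 gives 0.534. Events = 41×(0.737 + 0.534) = 52.
- Log-rank power (Schoenfeld) = Φ(√d·|ln HR|/2 − z).

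| HR | Events d | One-sided 0.19 | Two-sided 0.05 |
|---|---|---|---|
| 0.56 | 52 | 0.89 | 0.56 |
| 0.60 | 53 | 0.84 | 0.46 |
| 0.70 | 55 | 0.67 | 0.26 |
| 0.80 | 57 | 0.49 | 0.13 |

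A comparison is feasible, so lack of events does not explain the omission. The range 0.13 to 0.89 shows how much depends on the effect and on the alpha and sidedness that are left unstated. With 52 events, a 95% interval for the hazard ratio reaches a factor of about exp(1.96×2/√52) = 1.72 either side of the estimate.

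**4. Size of the clock difference.** Nine months is 9×30.44 = 274 days, and 14/274 = 5.1%. If one arm waited the full 14 days and the other none, with identical progression from randomization, the ratio of medians measured from start of therapy would be (274 − 14)/274 = 0.95. For 7 days it is 0.97, and for 3 days 0.99.

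**5. Effect of scan timing.** That calculation treats progression as observed continuously. Sections 4.0 and 11.1 put scans every 8 weeks and tie them to cycles, so progression dates follow the treatment clock. Take the same extreme case, exponential progression with a 274-day median (mean 274/ln 2 = 395 days) and scans every 56 days from start of therapy.

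- No delay: the cumulative probability is 0.43 by day 224 and 0.51 by day 280, so the median is 280 days.
- 14-day delay: it is 0.45 by day 238 and 0.52 by day 294 from randomization. The median is 294 days from randomization and 280 from start.
- Mean, no delay: 56/(1 − exp(−56/395)) = 424 days.
- Mean, 14-day delay: 0.965×424 + 0.035×56 = 411 days from start, and 411 + 14 = 425 from randomization.

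From start of therapy, the medians agree (280 and 280) but the means differ (424 and 411). From randomization, the medians differ (280 and 294) but the means agree (424 and 425). The effect is small, and its direction depends on the summary measure.

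**The case against.** **The Kaplan-Meier plan is not empty.** Curves by arm would give each median, which is the quantity in hypothesis 1, and allow a descriptive contrast. Progression and death are also components of TFF40, which is formally compared. Both points stand, so it would be wrong to say that the plan yields no PFS information. What is missing is a stated test or effect measure.

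**The clock matters little.** Section 6.16 caps the gap at 14 days, and the scan schedule makes the direction of any distortion uncertain. This stands, and it makes the origin a consistency point.

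**Two stronger readings a reader might infer.** One is that Arm A patients start later because they need ascorbic acid delivered. The documents give no start delay by arm. Section 6.19b lists study drug on site among the registration requirements, and both arms obtain pazopanib commercially (15.18). Only the scheduling of infusions differs, and its effect on start date is not stated. The other is that the start-of-therapy clock is what takes PFS off the randomized comparison. It is not: OS and TFF40 run from randomization and are still limited to eligible, treated patients, so changing the clock would not by itself restore a full randomized comparison.

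**Conclusion.** The point holds on the missing comparison. Objectives 2.22 and 2.24 promise a comparison between arms, and Sections 16.322 and 16.324 supply no method for one. This rests on the text alone and needs no assumption. The primary TFF40 test and decision rule are not affected.

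The time origin is a genuine but minor inconsistency: 0 to 14 days per patient, at most about 5% of a 9-month median, with no documented imbalance between arms. It would not justify an amendment alone, but is easily corrected in the same edit.

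The event and power figures rest on exponential PFS, a 9-month control median, uniform accrual and no dropout. They show that a comparison is feasible; they are not design values.

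**What to change.** - **Section 16.322:** define PFS from randomization. Add a between-arm log-rank test, a Cox hazard ratio with confidence interval, and median PFS per arm. State sidedness and alpha, since the one-sided 0.19 in Section 16.21 is set for TFF40 only.
- **Stratification, if used:** the Section 5.0 factors give 3×2 = 6 strata for 82 patients. State a pooling rule or an unstratified fallback, and treat OS the same way, because Section 16.321 does not describe its log-rank test as stratified.
- **Section 16.324:** name a between-arm method for duration on pazopanib, or reword objective 2.24 as descriptive.
- **Optional:** a sensitivity analysis of PFS in all randomized patients, which addresses the treated-only restriction that the clock change leaves in place. It depends on follow-up of patients who never start, for whom Section 13.7 currently ends data submission.

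The cost is a few added sentences. The main changes need no new data, since the randomization date is already the origin for OS and TFF40. The downside is modest power for PFS at conventional alpha, so the hazard ratio and its interval should carry the interpretation.
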